3.4.5 Duration of Subject Participation

Patients may continue treatment until radiographic progressive disease, withdrawal of consent, the occurrence of unacceptable toxicity, or a determination by the investigator the patient is not clinically benefiting. As per the patient's physician, when the participant requires care that is not allowed on study, the participant will discontinue treatment and enter the long-term follow-up period. While the patient and/or physician may decide prematurely to cease taking randomized therapy at any time, full follow-up of all randomized patients for the intended duration of the trial is planned by design for the collection of rPFS and OS data.

It is anticipated that it will take approx. 14 months to randomize the required 814 patients in the study. After the last patient is randomized patients will be followed for up to 24 months or at least until 508 deaths have occurred. The maximum duration of the study, from first date of randomization to last follow-up, will therefore be approximately 38 months.

After final analysis of the OS primary endpoint, long-term follow-up will be extended until a separate long-term safety follow-up study is available in the respective country, until patient death or until patient withdrawal of consent, whichever occurs first. The maximum duration of the study, from first date of randomization to last follow-up, will therefore be up to approximately 66 months.

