5.3.2 Safety Populations

- **PSMA-11 Safety Analysis Set:** All patients who received a dose of ⁶⁸Ga-PSMA-11. This includes screened patients that are not enrolled (i.e., not randomized). Patients enrolled will be included in the treatment arm to which they were randomized.

- **FAS Safety Analysis Set:** The subset of patients in the FAS who received at least one dose of randomized treatment. Patients will be included in the treatment arm corresponding to the actual treatment received.

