9.2.1 Definition of Treatment Emergent Adverse Events (TEAEs)

⁶⁸GA-PSMA-11

PSMA-617-01 SAP Version 3.0
18Jan2021

Page 53 of 79

This information is confidential or privileged information and trade secrets of Endocyte, Inc.

A ^{68}Ga -PSMA-11 TEAE is defined as an AE that was not present prior to dosing with ^{68}Ga -PSMA-11 but appeared following dosing, or was present at time of dosing but worsened during or after dosing.

The treatment-emergent period will be defined as the period from the date of ^{68}Ga -PSMA-11 dosing up to 6 days after the date of ^{68}Ga -PSMA-11 dosing as long as prior to the first dose of ^{177}Lu -PSMA-617 for the investigational arm and prior to Cycle 1 Day 1 for the BSC/BSoc arm.

AEs reported as "possibly", "probably", or "definitely" related to ^{68}Ga -PSMA-11 that occur beyond the 6-day reporting window but occur before the initiation of randomized treatment are also ^{68}Ga -PSMA-11 TEAEs. Unrelated ^{68}Ga -PSMA-11 AEs that occur beyond 6 days will not be TEAEs.

Randomized treatments

A randomized treatment TEAE is defined as an AE that was not present prior to initiation of randomized treatment, defined as first dose of ^{177}Lu -PSMA-617 for the investigational arm and Cycle 1 Day 1 for the BSC/BSoc arm, but appeared following treatment, or was present at treatment initiation but worsened during treatment. An AE that was present at treatment initiation but resolved and then reappeared while the patient was on treatment is a TEAE (regardless of the intensity of the AE when the treatment was initiated).

The treatment-emergent period will be defined as the period from the date of initiation of randomized treatment up to 30 days after the date of the last administration of randomized treatment or the day prior to the initiation of subsequent anticancer treatment, whichever occurs first.

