9.3 Clinical Laboratory Determination

Local labs will perform hematology, chemistry, serum testosterone, and urinalysis testing. The following laboratory parameters are to be summarized:

- Testosterone
- Chemistry

sodium	LDH	Bicarbonate ¹
potassium	blood urea	calcium
total and direct bilirubin	nitrogen ²	glucose
ALP	creatinine	total protein
AST	urate	albumin
ALT	phosphate	
	chloride	
- Urinalysis³

urine pH	glucose
protein content	ketones
specific gravity	
appearance and color	
- Hematology

complete blood count (white blood cell count and differential)
red blood cell count
hemoglobin
hematocrit
platelet count

1. total carbon dioxide or equivalent is acceptable

2. urea is acceptable

3. Urinalysis parameters are only collected at screening. Appearance and color, glucose, ketones and protein content are captured as free-text and will only be listed (not summarized).

Hematology, chemistry and serum testosterone laboratory values and the change from baseline during randomized treatment will be summarized for each parameter by visit. Shift tables of the worst post-baseline on-treatment laboratory toxicity based on CTCAE v5.0 grading relative to baseline will be presented as well as the frequency of grade 3/4 toxicities. For laboratory tests where CTCAE grades are not defined, shift tables using low/normal/high/(low and high) classification to compare baseline to worst post-baseline on-treatment value will be presented. Frequency statistics for qualitative laboratory parameters will also be presented by visit. The summaries will include all laboratory assessments collected no later than 30 days after the last administration of randomized treatment (i.e. on-treatment).

The mean (\pm standard error) values over time will be plotted for hemoglobin, hematocrit, platelets, WBC, absolute neutrophil count, AST, ALT, BUN, and creatinine by treatment arm.

An additional summary of hematology, chemistry and serum testosterone laboratory values at screening will be provided for the PSMA-11 Safety Analysis Set.

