Listings of all laboratory data and listings of laboratory toxicities \geq Grade 3 will be provided. Values outside of the laboratory's reference range will be flagged. Values collected later than 30 days after the last randomized treatment date will also be flagged. If laboratory values are provided as '<X' (i.e. below limit of detection) or '>X', prior to conversion of laboratory values to SI unit, these numeric values are set to X. The patient listings will indicate the CTCAE grade.

During long-term follow up, hematology and chemistry are collected every 3 months. Shift tables of the worst post-baseline laboratory toxicity during LTFU based on CTCAE v5.0

grading relative to baseline will be presented as well as the frequency of grade 3/4 toxicities. For laboratory tests where CTCAE grades are not defined, shift tables using low/normal/high/(low and high) classification to compare baseline to worst post-baseline value during LTFUP will be presented. These will be displayed in similar tables separately for LTFU using the FAS Safety Analysis Set. Laboratory assessments collected during LTFU will be included in the listings.

Liver function parameters

Liver function parameters of interest are total bilirubin (TBL), ALT, AST and alkaline phosphatase (ALP). The number (%) of patients with worst post-baseline values will be summarized by treatment arm using the FAS Safety Analysis Set only. The following summaries will be produced during the randomized treatment and long-term follow up, separately:

- ALT > 3xULN
- ALT > 5xULN
- ALT > 8xULN
- ALT > 10xULN
- ALT > 20xULN
- AST > 3xULN
- AST > 5xULN
- AST > 8xULN
- AST > 10xULN
- AST > 20xULN
- ALT or AST > 3xULN
- ALT or AST > 5xULN
- ALT or AST > 8xULN
- ALT or AST > 10xULN
- ALT or AST > 20xULN
- TBL > 2xULN
- TBL > 3xULN
- Concurrent ALT > 3xULN & TBL > 2xULN
- Concurrent AST > 3xULN & TBL > 2xULN
- Concurrent ALT or AST > 3xULN & TBL > 2xULN
- Concurrent ALT or AST > 3xULN & TBL > 2xULN & ALP < 2xULN
- Concurrent ALT or AST > 3xULN & TBL > 2xULN & ALP ≥ 2xULN

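### Long-term follow-up laboratory and liver tables are not split at subsequent anti-cancer therapy, so toxicity of later drugs is mixed with late effects of study treatment, in a direction the documents do not fix

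*SAP*

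**What the plan says.** SAP 9.3 summarizes LTFU laboratory data by "Shift tables of the worst post-baseline laboratory toxicity during LTFU based on CTCAE v5.0", together with the frequency of grade 3/4 toxicities. It adds that "These will be displayed in similar tables separately for LTFU using the FAS Safety Analysis Set". For the liver parameters, "The number (%) of patients with worst post-baseline values will be summarized by treatment arm using the FAS Safety Analysis Set only", and "The following summaries will be produced during the randomized treatment and long-term follow up, separately". No sentence in SAP 9.3 stops or divides any of these tables at the start of a new anti-cancer therapy.

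The arm in these tables is not the randomized arm. For the FAS Safety Analysis Set, SAP 5.3.2 states: "Patients will be included in the treatment arm corresponding to the actual treatment received".

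The SAP does use the new-therapy date elsewhere. In SAP 9.2.1 the treatment-emergent window for adverse events (AEs) runs to 30 days after the last administration "or the day prior to the initiation of subsequent anticancer treatment, whichever occurs first". SAP 5.2 has a rule for partial dates of subsequent therapy, but only for assigning AEs as treatment-emergent.

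On the clinical side, Protocol 3.4.5 says that "when the participant requires care that is not allowed on study, the participant will discontinue treatment and enter the long-term follow-up period". Protocol 5.3.2 lists cytotoxic chemotherapy, immunotherapy and other systemic radioisotopes among the prohibited treatments. Protocol 3.4.4 places the end-of-treatment visit before any such therapy begins. Protocol Appendix 1 (Tables 4 and 6) has hematology, chemistry and the start and stop dates of new treatments collected about every 3 months in LTFU.

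**The concern.** By design, LTFU is the period in which treatments barred on study begin. Several of these can themselves affect blood counts or liver tests. A worst-value summary is especially exposed, because one abnormal result after a later drug fixes the patient's grade for the whole period, whatever caused it. That result is then counted under the study arm.

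At stake is the reading of late marrow, renal and liver safety. A reader who compares the two columns will tend to take the difference as late toxicity of 177Lu-PSMA-617, when part of it may reflect different use or timing of later drugs. The SAP recognizes this problem for treatment-emergent AEs by cutting at the new-therapy date. It does not carry the idea into LTFU, where attribution is harder.

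**Working it through.** The plan states no figure on this point, so there is nothing to reproduce. The check has three parts.

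**1. Which windows use the new-therapy date**

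| Output | End of window | Uses new-therapy date? |
|---|---|---|
| Randomized-treatment AEs (SAP 9.2.1) | 30 days after last administration, or day before new therapy if earlier | Yes |
| On-treatment laboratory tables (SAP 9.3) | 30 days after last administration | No |
| LTFU laboratory shift and grade 3/4 tables (SAP 9.3) | All of LTFU | No |
| LTFU liver tables (SAP 9.3) | All of LTFU | No |
| LTFU AE tables (SAP 9.2.6) | All of LTFU | No |

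The date needed for a split is already collected (Protocol Appendix 1).

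**2. How far the mixing could move a table**

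All inputs here are assumptions; none is in the documents. Let b be the background share of patients with a grade 3/4 worst value, l the late 177Lu-PSMA-617 effect (0 in control), s the share starting later chemotherapy, and c the share of those with grade 3/4 toxicity from it. With independent causes,

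share = 1 - (1 - b)(1 - l)(1 - s·c).

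Take b = 3%, l = 5%, c = 30%. Without later therapy the investigational arm shows 1 - 0.97 × 0.95 = 7.85% against 3.00%, a difference of +4.85 points and a risk ratio of 2.62. With later chemotherapy included:

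| Later chemotherapy, investigational / control | Investigational | Control | Difference | Risk ratio |
|---|---|---|---|---|
| 20% / 40% | 1 - 0.97 × 0.95 × 0.94 = 13.4% | 1 - 0.97 × 0.88 = 14.6% | -1.3 points | 0.91 |
| 20% / 20% | 13.4% | 1 - 0.97 × 0.94 = 8.8% | +4.6 points | 1.52 |
| 40% / 20% | 1 - 0.97 × 0.95 × 0.88 = 18.9% | 8.8% | +10.1 points | 2.14 |

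So the same late effect can be reversed, left nearly unchanged as a difference but diluted as a ratio, or roughly doubled as a difference.

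Over a wider assumed grid (b = 3%; l = 3%, 5% or 8%; c = 15% or 30%; later chemotherapy 20/20, 20/40, 30/50 or 40/20 percent), true differences of +2.9 to +7.8 points become -3.2 to +12.6 points.

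**3. Whether the design figures fix the direction**

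Protocol 8.3 assumes median rPFS of 4 months (control) and 6 months (investigational), and median OS of 10 and 13.7 months. Assume exponential times and exit from treatment at radiographic progression. The mean time alive after progression within T months of follow-up is then the restricted mean OS minus the restricted mean rPFS, where for median m

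restricted mean = (m / ln 2)(1 - 2^(-T/m)).

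| T (months) | Control | Investigational |
|---|---|---|
| 20 | 10.82 - 5.59 = 5.23 | 12.58 - 7.80 = 4.78 |
| 27 | 12.21 - 5.72 = 6.49 | 14.72 - 8.27 = 6.45 |
| 38 | 13.39 - 5.76 = 7.63 | 16.88 - 8.55 = 8.33 |

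Here 20 = 14 months' accrual + 6 months' minimum follow-up, 27 = 14 + 13 (both Protocol 8.3), and 38 is the pre-extension study duration in Protocol 3.4.5. Control has slightly more time after progression early, the arms are about equal at 27 months, and the order then reverses. The design does not imply a large or lasting control excess.

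**The case against.** A reader might infer that control patients leave treatment sooner, spend more of LTFU on later drugs, and so hide late 177Lu-PSMA-617 toxicity. The documents do not support that as a stated direction. They give no later-therapy rates, and the design medians yield only a small early difference that later reverses. Many early control dropouts withdrew consent to follow-up (Protocol 3.1.1) and would contribute no LTFU values. Patients had already had one or two taxane regimens, so heavy later chemotherapy cannot be presumed. Needing prohibited care is also only one route into LTFU.

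A reader might also infer that these tables are the only source for late safety, or that SAP 9.3 breaks a rule the SAP otherwise follows. Neither holds. LTFU AEs are tabulated (SAP 9.2.6). The current protocol also requires renal toxicities, secondary malignancies and related serious events in LTFU to be assessed for causality (Protocol 7.2). Later therapies are summarized and listed (SAP 9.8), and laboratory values of grade 3 or higher and abnormal liver values are listed by patient (SAP 9.3). The plan cuts treatment-emergent AEs and reports LTFU as observed, which is a consistent convention.

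Finally, a pre-therapy cut has its own bias. Truncation at new therapy is tied to progression, values before it may be few, and a true late radioligand effect that appears after switching would be lost.

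These objections limit the claim but do not remove it. The listings allow case-by-case review, but they do not separate the two sources of toxicity in the by-arm tables. The last objection argues for adding panels, not for replacing the existing tables.

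**Conclusion.** The point holds in a limited form. SAP 9.3 tabulates worst laboratory grade, grade 3/4 frequency and liver thresholds over all of LTFU, by treatment received, with no split at subsequent anti-cancer therapy, although treatments prohibited on study begin in that period. Later-drug toxicity and late study-treatment effects cannot be told apart in these tables.

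The resulting bias can go either way. The percentages in the working show what is possible under assumed rates and are not estimates for this trial. They assume independent causes and ignore differences in time at risk.

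The tables are descriptive, carry no hypothesis test, and affect no primary or key secondary conclusion. The change is worth making because it is cheap and improves the reading of late safety; leaving it undone does not undermine the trial.

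**What to change.** - Keep the all-LTFU tables in SAP 9.3. Add the same shift, grade 3/4 and liver tables in two panels: values up to the day before the first subsequent anti-cancer therapy, and values on or after that date.
- Use the start dates already collected, and extend the partial-date rule in SAP 5.2 to this purpose.
- In each panel, show per arm the number of patients with at least one value and the follow-up time.
- Apply the same split to the LTFU AE tables in SAP 9.2.6 where dates allow. That section says only term and grade are captured, so the split may not be feasible for every event.
- State that conclusions on late toxicity are read from all panels together, not from the pre-therapy panel alone.

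The cost is a few sentences of SAP text and some extra tables, with no new data collection. The downsides are sparse values in the pre-therapy panel and truncation there that is linked to progression; a table footnote should say so.

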9.3.1 Sub-study

Shift tables as described above will be presented using the Sub-study Safety Analysis Set. Listings of all laboratory data will be provided using the PSMA-11 Sub-study Analysis Set. Hematology and chemistry data collected during long-term follow up will be listed using the Sub-study Safety Analysis Set.

9.4 Vital Signs, Physical Findings, and ECG

Vital signs (blood pressure, pulse, and respiratory rate) and weight, will be summarized by visit (observed and change from baseline during randomized treatment). The summaries will include all assessments collected no later than 30 days after the last

administration of randomized treatment (i.e. on-treatment). For those treated with ¹⁷⁷Lu-PSMA-617, the vital sign taken at 15 minutes pre-dose during the first 6 cycles will be used for the summary of changes by visit. The number (%) of patients with notable vital signs during randomized treatment (high/low) will be presented by treatment arm and overall using the FAS Safety Analysis Set. An additional summary of vital signs at screening will be provided using the PSMA-11 Safety Analysis Set. The clinically notable vital sign criteria are provide below:

Vital Sign (unit)	Clinically notable criteria	
	Above normal value	Below normal value
Weight (kg)	Increase > 10% from baseline	Decrease > 10% from baseline
Systolic blood Pressure (mmHg)	>=180 with increase from baseline of >=20	<=90 with decrease from baseline of >=20
Diastolic blood Pressure (mmHg)	>=105 with increase from baseline of >=15	<=50 with decrease from baseline of >=15
Pulse rate (bpm)	>=100 with increase from baseline of >25%	<=50 with decrease from baseline of >25%

ECOG performance status and change from baseline classified as improved, no change and worsened will be summarized as a categorical variable by visit for the FAS Safety Analysis Set only.

ECG will be done at screening only. Overall ECG interpretation will be summarized. PR, RR, and QRS Intervals and heart rate will be summarized as continuous variables. QTc, as captured on the CRF, will not be summarized as the correction method is site specific and will be recorded in the TMF. QTc will only be included in the listings with the correction method "unspecified." The number (%) of patients with notable ECG values at screening will also be presented using the PSMA-11 Safety Set and the FAS Safety Set:

Clinically notable ECG values	
HR	
 Value of > 120 bpm Value of < 40 bpm
PR	
 Value of > 200 ms
QRS	
 Value of > 110 ms

Abnormal findings from physical examinations will be assessed for clinical significance and will be presented in the AE listings and tables as appropriate.

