Appendix 1 Schedules of Assessments

Table 3 Schedule of assessments: ^{177}Lu -PSMA-617 plus best supportive/best standard of care arm (Cycle 1)

Study Period:	Cycle 1					
	Week 1	Week 2	Week 3	Week 4	Week 5	Week 6
Cycle Week:	Day 1	Day 8	Day 15	Day 22	Day 29	Day 36
Concomitant medication review	X-----					X
AE monitoring ^a	X-----					X
Weight	X ^b					
ECOG	X ^b					
Directed physical exam	X ^b					
Vital signs ^c	X ^b					
EQ-5D-5L	X ^{d,f}					
FACT-P	X ^{d,f}					
BPI-SF	X ^{d,f}					
Administer ^{177}Lu -PSMA-617	X					
Best supportive/best standard of care	As per physician's orders					
Hematology ^e	X ^b	X ^b	X ^b	X ^b	X ^b	X ^b
Chemistry ^e	X ^b	X ^b	X ^b	X ^b	X ^b	X ^b
Serum/plasma testosterone	X ^b					
PSA	X ^b					
Radiographic imaging (CT with contrast/MRI and bone scan)	Every 8 weeks (\pm 4 days) after first dose of ^{177}Lu -PSMA-617 for the first 24 weeks (independent of dose delays), then every 12 weeks (\pm 4 days)					

^a Adverse event monitoring will commence at time of consent.

^b Can be done up to 3 days prior to Day 1. For hematology and chemistry: up to 3 days prior to Days 1, 8, 15, 22, 29, and 36.

^c Blood pressure, pulse and respiratory rate will be assessed at required physical exams (up to 3 days of Day 1) and at 15(+/-5) minutes before, 30 (+/-5) minutes post, and 60 (+/-5) minutes post ^{177}Lu -PSMA-617 administration.

^d To be completed prior to drug administration on Day 1. Can be completed up to 3 days prior to Day 1.

^e Hematology and chemistry to be done every week for Cycle 1 only.

^f HRQoL and pain assessments may be self-completed by subject or administered in interview format and completed by a caretaker, clinician or site research team member.

AE = adverse event; BPI-SF Brief Pain Inventory – Short Form; CT = computed tomography; ECOG = Eastern Cooperative Oncology Group; EQ-5D-5L = European Quality of Life (EuroQol) – 5 Domain 5 Level scale; FACT-P = Functional Assessment of Cancer Therapy – Prostate; MRI = magnetic resonance imaging; PSA = prostate-specific antigen

Table 4 Schedule of assessments: ^{177}Lu -PSMA-617 plus best supportive/best standard of care arm (Cycles 2 to LTFU)

Study Period:	Cycles 2-6*						After Cycle 6**	End of Treatment ^g	Long-term follow-up (Before final analysis of alternate primary endpoint OS)	Long-term follow-up Extension (after final analysis of primary alternate endpoint OS)

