If the patient meets the criteria above, and agrees to continue with additional treatment of ¹⁷⁷Lu-PSMA-617, the investigator may administer a further 2 cycles. A maximum of 6 cycles of radioligand therapy is allowed. If the patient does not meet all of the criteria or does not agree to additional ¹⁷⁷Lu-PSMA-617 treatment, then no additional doses of ¹⁷⁷Lu-PSMA-617 will be administered after Cycle 4. After the last cycle of ¹⁷⁷Lu-PSMA-617, patients can continue best supportive/best standard of care alone.

** Cycles 2-6 are 6 weeks long. Cycle 7 Day 1 should occur after 6 full weeks from C6D1 (Day 43 of Cycle 6). Starting with Cycle 7, all cycles are 12 weeks long. The stipulated windows apply to C7D1 required procedures and for all cycles afterwards.

^a Phone evaluations are allowed, but are not required for visits after Day 1 of each cycle.

^b Adverse event monitoring will commence at time of consent.

^c Can be done up to 3 days prior to Day 1. For hematology and chemistry: up to 3 days prior to Days 1, 15, and 29.

^d Blood pressure, pulse and respiratory rate will be assessed at required physical exams (up to 3 days of Day 1) and at 15(+/-5) minutes before, 30(+/-5) minutes post, and 60(+/-5) minutes post ¹⁷⁷Lu-PSMA-617 administration.

^e To be completed prior to drug administration (if applicable) on Day 1. Can be completed up to 3 days prior to Day 1.

^f For Cycles 2 to 6: Hematology and chemistry to be done at Days 1, 15, and 29 (every 2 weeks). After Cycle 6, to be done on Cycle 7 Day 1 and then every 12 weeks (\pm 4 days).

^g To be done once a patient is to enter the long-term follow-up part of the study. To occur approximately 30 days from the last dose of ¹⁷⁷Lu-PSMA-617 or last dose or intervention of best supportive/best standard of care end of treatment decision, but before the initiation of subsequent anticancer treatment, outside of what is allowed on study

^h HRQoL and pain assessments may be self-completed by subject or administered in interview format and completed by a caretaker, clinician or site research team member.

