AE = adverse event; ANC = absolute neutrophil count; BPI-SF Brief Pain Inventory – Short Form; CBC = complete blood count; CT = computed tomography; ECOG = Eastern Cooperative Oncology Group; EQ-5D-5L = European Quality of Life (EuroQol) – 5 Domain 5 Level scale; FACT-P = Functional Assessment of Cancer Therapy – Prostate; MRI = magnetic resonance imaging; PSA = prostate-specific antigen; PSMA = prostate-specific membrane antigen; WBC = white blood cell

Table 5 Schedule of assessments: Best supportive/best standard of care only arm (Cycle 1)

Study Period:	Cycle 1					
	Week 1	Week 2	Week 3	Week 4	Week 5	Week 6
Cycle Week:	Day 1	Day 8	Day 15	Day 22	Day 29	Day 36
Concomitant medication review	X-----					X
AE monitoring ^b	X-----					X
Weight	X ^a					
ECOG	X ^a					
Directed physical exam	X ^a					
Vital signs ^c	X ^a					
EQ-5D-5L	X ^{d,f}					
FACT-P	X ^{d,f}					
BPI-SF	X ^{d,f}					
Best supportive/ best standard of care	As per physician's orders					
Hematology ^e	X ^a	X ^a	X ^a	X ^a	X ^a	X ^a
Chemistry ^e	X ^a	X ^a	X ^a	X ^a	X ^a	X ^a
Serum/plasma testosterone	X ^a					
PSA	X ^a					
Radiographic imaging (CT with contrast/MRI and bone scan)	Every 8 weeks (\pm 4 days) after Cycle 1 Day 1 ^g for the first 24 weeks (independent of dose delays), then every 12 weeks (\pm 4 days) through the End of Treatment visit					

^a Can be done up to 3 days prior to Day 1. For hematology and chemistry: up to 3 days prior to Days 1, 8, 15, 22, 29, and 36.

^b Adverse event monitoring will commence at time of consent.

^c Blood pressure, pulse and respiratory rate will be assessed at required physical exams (up to 3 days of Day 1).

^d To be completed prior to any drug administration (if applicable) on Day 1. Can be completed up to 3 days prior to Day 1.

^e Hematology and chemistry to be done every week for Cycle 1 only.

^f HRQoL and pain assessments may be self-completed by subject or administered in interview format and completed by a caretaker, clinician or site research team member.

^g Cycle 1 Day 1 for patients on the Best supportive/best standard of care only arm is considered as the day that the majority of the day 1 assessments are conducted

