Note: The reference date for safety assessments during randomized treatment (e.g. adverse event onset, laboratory measurement, vital sign measurement, ECOG performance status, etc.) is the date of first dose of randomized treatment and the reference date for efficacy assessments (i.e. survival, tumor response, health related

quality of life) is the date of randomization. The reference date for all assessments in the sub-study is the date of first dose of ¹⁷⁷Lu-PSMA-617.

Baseline for a given variable will be defined as the last non-missing assessment, including unscheduled assessments, for that variable obtained prior to or on the reference date but before the first treatment dose, unless otherwise noted.

For efficacy evaluations, the last non-missing assessment, including unscheduled assessments on or before the date of randomization is taken as "baseline" value or "baseline" assessment. For RECIST/PCWG3-based endpoints using CT/MRI, and bone scans (i.e. rPFS, ORR, DCR, duration of response, PFS), a window of 28 days from the start of randomized treatment will be allowed, i.e. the investigator/central review-reported responses will be maintained and baseline considered valid if the baseline assessment is within 28 days of randomized treatment start date. In the context of baseline definition, the efficacy evaluations also include the laboratory parameters PSA, ALP and LDH, and HRQoL (e.g. FACT-P). For safety evaluations of randomized treatment (i.e. laboratory assessments, ECOG performance status and vital signs), the last available assessment on or before the date of start of randomized treatment is taken as "baseline" assessment. For vital signs where time of assessment is captured (e.g. pre-dose and post-dose vital sign), the 15 minutes pre-dose value on or before the date of start of randomized treatment is taken as "baseline" assessment. For safety evaluations of ⁶⁸Ga-PSMA-11 (i.e. laboratory assessments and vital signs), the last available assessment on or before the date of ⁶⁸Ga-PSMA-11 is taken as "baseline" assessment.

In rare cases where multiple measurements meet the baseline definition, with no further flag or label that can identify the chronological order, then the following rule should be applied: If multiple values are from the same laboratory or collected for ECGs or vital signs, then the last value should be considered as baseline.

If patients have no value as defined, the baseline result will be considered as missing.

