5.1.2 Visit Windows

For data collected at multiple time points, the scheduled collection date/time will be used to summarize the data, unless otherwise indicated. Visits are scheduled from time of previous cycle's Day 1.

Scan assessments are scheduled from the reference date (date of first dose). Scan dates are not associated with a visit number. Dates are used for analyses and patient listings.

Unscheduled assessments will not be taken into account in summary variable calculations, except for baseline assessments and unscheduled RECIST, bone scan, PSA and HRQoL evaluations for evaluating efficacy (Section 8). All measurements will be presented in the listings.

Unless otherwise indicated, if more than one measurement (a lab result for example) exists for a patient on a particular time point/visit, the last value obtained at that time point/visit will be used when summarizing the data.

Refer to protocol section 6.1 and protocol Appendix 1 for schedules of study assessments during each study period.

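### SAP 9.4 does not say which readings feed the by-arm count of notable blood pressure and pulse; if all of them count, the investigational arm is flagged more often even with no drug effect

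*SAP*

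**What the plan says.** **Schedule.** In Protocol Appendix 1, the Table 3 footnote on vital signs (investigational arm, Cycle 1) asks for readings at the physical exam and "at 15(+/-5) minutes before, 30 (+/-5) minutes post, and 60 (+/-5) minutes post" each administration. The Table 4 footnote repeats this for Cycles 2 to 6: "30(+/-5) minutes post, and 60(+/-5) minutes post". For the control arm, Tables 5 and 6 ask for the exam reading alone: "Blood pressure, pulse and respiratory rate will be assessed at required physical exams (up to 3 days of Day 1".

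**Summaries.** SAP 9.4 describes by-visit summaries of vital signs and weight, then states their scope: "The summaries will include all assessments collected no later than 30 days after the last" administration of randomized treatment. For patients given the radioligand it adds one restriction: "the vital sign taken at 15 minutes pre-dose during the first 6 cycles will be used for the summary of changes by visit". The next sentence introduces the table at issue: "The number (%) of patients with notable vital signs during randomized treatment (high/low) will be presented by treatment arm and overall". No rule on choice of reading accompanies that sentence. The criteria cover weight, systolic and diastolic pressure and pulse, and each requires a change from baseline.

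**Baseline.** Under SAP Section 5, where the time of a reading is captured, "the 15 minutes pre-dose value on or before the date of start of randomized treatment is taken as" baseline. Otherwise baseline is the last assessment on or before the start of randomized treatment.

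**General default.** SAP 5.1.2 says that, unless otherwise indicated, when several measurements exist at one time point or visit, "the last value obtained at that time point/visit will be used when summarizing the data".

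**The concern.** The SAP puts the two arms on the same footing for one vital-sign output and leaves the neighbouring one open. A count of patients with any value beyond a limit rises with the number of readings taken. The investigational arm has three or four readings per dosing cycle, two of them after the infusion, and control has one. If every reading is eligible, measurement frequency alone raises the investigational count. If only the last reading is eligible, the investigational arm supplies a value taken an hour after the dose. That value follows the same-day antiemetic treatment recommended in Protocol 5.1.3 and possibly the optional saline of Appendix 2.

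This is the SAP's only by-arm threshold table for on-treatment blood pressure and pulse. Its readers could take an artefact of the schedule for a drug effect. Two programmers working from the SAP could also produce different tables.

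**Working it through.** The plan states no rate, power or sample size for this table, so there is no figure of its own to reproduce. The check is a count of scheduled readings, followed by a calculation under no drug effect with the same number of cycles in both arms.

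**1. Scheduled readings.** Investigational: 3 per dosing cycle if the exam and pre-dose readings coincide, otherwise 4. Control: 1. Over 6 cycles that is 18–24 against 6; over 4 cycles, 12–16 against 4.

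**2. Remove readings that cannot be notable.** The Cycle 1 pre-dose reading is the investigational baseline, and any Cycle 1 exam reading precedes it. The Cycle 1 exam reading is the control baseline. Cycle 1 therefore contributes 2 readings against 0. With *c* dosing cycles:

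- Investigational: 2 + 3(*c* − 1) to 2 + 4(*c* − 1). For *c* = 6 this is 17 to 22; for *c* = 4 it is 11 to 14.
- Control: *c* − 1, which is 5 or 3.

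**3. Independence bound.** With per-reading probability *p* (assumed) and *k* readings, P(any notable) = 1 − (1 − *p*)^*k*. For *p* = 1% and 6 cycles, control is 1 − 0.99^5 = 4.9%, and investigational is 1 − 0.99^17 = 15.7% to 1 − 0.99^22 = 19.8%. Across *p* = 0.5–2% and 4 or 6 cycles, control is 1.5–9.6% and investigational 5.4–35.9%. This is an upper bound, because readings taken within about 75 minutes in one patient are far from independent.

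**4. Correlated readings.** The simulation used 300,000 patients per setting, with normal patient, visit and within-visit components and the SAP systolic and pulse criteria. Assumed values: systolic mean 135 with between-patient SD 14; pulse mean 78 with between-patient SD 11. Percentage of patients flagged high over 6 cycles:

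| Measure (visit SD, within-visit SD) | Control | Investigational, all readings | Ratio | Pre-dose only | 60-minute only |
|---|---|---|---|---|---|
| Systolic (12, 3) | 1.94 | 2.77–2.99 | 1.4–1.5 | 1.95 | 1.93 |
| Systolic (10, 7) | 1.83 | 3.68–4.28 | 2.0–2.3 | 1.82 | 1.84 |
| Systolic (8, 10) | 2.21 | 5.38–6.36 | 2.4–2.9 | 2.27 | 2.47 |
| Pulse (9, 2) | 5.35 | 7.12–7.55 | 1.3–1.4 | 5.36 | 5.33 |
| Pulse (7, 5) | 3.99 | 7.65–8.80 | 1.9–2.2 | 4.04 | 4.02 |
| Pulse (5, 7) | 4.08 | 9.07–10.63 | 2.2–2.6 | 4.02 | 4.37 |

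The largest ratio is in a 4-cycle setting: systolic (8, 10), 4.48/1.44 = 3.1. The smallest is low pulse (9, 2) over 6 cycles, 6.38/4.88 = 1.3. So between 1 − 1/1.3 = 23% and 1 − 1/3.1 = 68% of flagged investigational patients would be flagged only because of the extra readings. Within-visit variability drives the size.

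**5. The two alternatives.** Using the pre-dose reading alone, the arms agree (all settings, high values: systolic 1.2–2.3% against 1.2–2.2%; pulse 2.6–5.4% in both). Using the 60-minute reading alone, they nearly agree when there is no drug or infusion-day effect (systolic 1.2–2.5% against 1.2–2.2%), but the two arms' values are taken under different conditions.

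**The case against.** The strongest objection is that the SAP nowhere says this table counts every reading. A reader might infer from the schedule that it does count three or four per cycle, and that an excess in the investigational arm is therefore certain. The documents do not support that as fact. SAP 5.1.2 supplies a default that could leave one reading per visit, and then the no-effect frequencies nearly match. This part of the objection stands, so the inflation is conditional on the reading adopted.

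The default does not settle the matter, though. It yields where something else is indicated, and SAP 9.4 speaks of all assessments. It also does not say whether the three timed readings around a dose are one time point or three. The neighbouring liver-test thresholds in SAP 9.3 use the worst post-baseline value, which makes counting any crossing the more natural reading here too. And if the default does apply, it selects the post-infusion value.

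A reader might also infer that a true acute infusion effect could never be told apart from the extra readings. That goes too far. The count alone cannot separate them, but SAP 5.1.2 lists all measurements, the by-visit change summary uses pre-dose values, and SAP 9.2.4 tabulates adverse events by cycle of onset.

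Finally, the table is descriptive, has no test attached, and any inflation from extra readings runs against the drug. Including post-infusion readings in a safety screen is itself defensible. All of this limits the importance of the point. It does not justify comparing arms on different measurement schedules without saying so.

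**Conclusion.** The point holds in conditional form. The schedules differ, and the pre-dose restriction does not reach the by-arm count of notable blood pressure and pulse. If all on-treatment readings count, a patient given six doses contributes 17–22 post-baseline readings through Cycle 6 against 5 in control (11–14 against 3 over four cycles), and more investigational patients are flagged with no drug effect. The factor of roughly 1.3 to 3.1 rests on assumed means, SDs and correlations, none of which the documents give, and on equal numbers of cycles. Diastolic pressure was not simulated, but it has the same schedule. If the last-value default applies, the frequency problem largely disappears and a mismatch in timing remains.

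The ratio of readings, about 3.4 to 4.4 (17/5 to 22/5 over six cycles), should not be read as the ratio of flagged patients, because repeated readings overlap. Nor is the whole table affected: weight is scheduled once per cycle in both arms, and the schedules match after Cycle 6. No efficacy result or formal test depends on this.

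**What to change.** Add a rule to SAP 9.4, for example:

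> *The between-arm table of notable blood pressure and pulse uses one post-baseline reading per scheduled visit. In the investigational arm this is the 15-minute pre-dose value at visits where 177Lu-PSMA-617 is given, and the exam value at every other visit, including cycles without a dose, Cycle 7 onward and End of Treatment. In the control arm it is the exam value. Notable values 30 and 60 minutes after dosing are shown in a separate table for the investigational arm, against the SAP-defined baseline and optionally also against the same-day pre-dose value.*

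Visits without a dose need explicit mention. Patients who stop the radioligand but stay on best supportive or standard care have no pre-dose reading, and a rule limited to pre-dose values would drop them from the comparison.

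The cost is this short rule and one extra single-arm table; no new data are needed. The small downside is that post-dose values leave the between-arm table, but they remain visible in the single-arm table and the listings.
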